Document: Statistical Analysis Plan

Official Study Title: Digital Community to Improve Health in Rural Areas

NCT Number: NCT05363865

Document Date: 03/04/2025

Statistical Analysis Plan – AG C-RCT

The statistical analyses will examine the intervention effect (i.e., experimental versus control) on the primary, secondary, and tertiary outcomes, with the covariate of individuals' drug use status (i.e., PWUD versus PWNUD) (see Table 1). The primary analyses will be conducted using the intention-to-treat (ITT) method. That is, all participants who completed the baseline measure will be included in the analyses by replacing missing data by carrying forward the last observation. We will perform multi-level modeling with clustered cohorts and report the intra-class correlations (ICC) of the cohort (i.e., group). In these models, we will specify 16 models with four sets of random effects models (i.e., random intercept only, random slope only, random intercepts and slopes without their correlations, and random intercepts and slopes with their correlations) and select the best one based on model-fit indices (i.e., AIC, BIC, and the likelihood ratio test).

The primary outcome is a composite score summing six yes/no behaviors promoted in the intervention: (a) HIV testing, (b) HCV testing, (c) HIV prevention, (d) requesting Naloxone before the assessment time point (i.e., the requests made at the immediate follow-up are counted for the 3-month follow-up), (e) carrying Naloxone, and (f) making or rebuilding at least one social connection. The assessment of HIV prevention depends on each participant's sexual risk and drug injection risk and includes PrEP use, use of condoms during sex, use of syringe service programs, and disinfecting injection equipment. Specifically, individuals engaging in sexual behaviors receive a score of 1 if they report using condoms during sexual encounters or using PrEP. Likewise, individuals at risk of drug injection receive a score of 1 if they report using PrEP, using syringe service programs, or disinfecting their injection equipment. For participants

who neither engage in sexual behaviors nor are at risk of drug injection, an HIV prevention score of 1 is recorded. The primary outcome is treated as a continuous variable, ranging from 0 to 6.

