For the secondary and tertiary outcomes (see Table 1), we will specify a binomial family for the analysis of binary data. For outcomes about change, such as substance use frequency, baseline responses will be subtracted from those obtained at the follow-up assessments (i.e., T1 – T0). We will impose no alpha correction/adjustment for multiple outcome comparisons because we have no conjunction hypotheses and these outcomes are not the primary outcome.

The design of the study allows for the assessment of the total effect of the Zoom sessions, GROV app, and HIV/HCV testing and Narcan kit availability. Therefore, that test is possible only for the immediate follow-up and will be conducted in an initial outcome paper that examines the efficacy of this multi-level program.

The 3-month and 6-month follow-ups provide an idea of the impact of the intervention when all participants have the option of receiving HIV/HCV testing and Narcan kits and also permit an examination of the durability of the effects. Therefore, these outcomes will be reported in a second paper.

We will carry out the following sensitivity analyses: (a) modified ITT analyses (i.e., including only those experimental participants who attended at least one session); (b) per-protocol analyses (i.e., including only data from participants who completed all three Zoom sessions originally allocated); and (c) analyses including relevant baseline measures, GROV activities, intervention process evaluation, fidelity assessment, and HIV/HCV testing and Narcan kit shipment schedules as covariates to assess the robustness of the results. The sensitivity analyses described here are not exhaustive, and new analyses can be added based on the research

team's decision (e.g., replacing the request data with the delivery/shipment data in the composite score).

We will also carry out process analyses by examining the content of the sessions with ChatGPT 4.0 (or later versions) and testing if these variables, as well as the number of sessions attended and GROV use, correlate with the study outcomes in the intervention group.

Table 1.
C-RCT Outcomes

Primary Outcome	Secondary Outcomes	Tertiary Outcomes

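### Sensitivity analysis (a) filters only the experimental arm on attendance and (b) gives no rule for controls, so agreement with ITT would not show robustness

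*SAP*

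**What the plan says.** The opening paragraph of the SAP sets the comparison as "the intervention effect (i.e., experimental versus control") and makes ITT primary: "all participants who completed the baseline measure will be included in the analyses by replacing missing data by carrying forward the last observation".

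The sensitivity-analysis paragraph then adds two attendance-based sets:

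- Rule (a) reads "modified ITT analyses (i.e., including only those experimental participants who attended at least one session"). It names the experimental arm only.
- Rule (b) reads "per-protocol analyses (i.e., including only data from participants who completed all three Zoom sessions originally allocated"). It speaks of participants in general.

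Neither says what a control must do to be included, and no weighting or complier method is described for either.

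The SAP does not say outright whether controls have Zoom sessions. The paragraph on the design describes the tested contrast as "the total effect of the Zoom sessions, GROV app, and HIV/HCV testing and Narcan kit availability". The process analyses ask whether "the number of sessions attended and GROV use, correlate with the study outcomes in the intervention group". The paragraph on the 3- and 6-month follow-ups mentions only testing and Narcan kits as open to everyone. All this suggests that controls have no sessions. On the other side, a tertiary outcome in Table 1 covers interactions inside as well as outside sessions, which could suggest that they do.

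**The concern.** Randomisation balances the whole arms, not the part of one arm that turns up. People who join group sessions may differ, with or without the programme, in whether they test, carry naloxone or make connections, and these make up much of the primary score. Dropping non-attenders from one arm puts that difference into the arm contrast.

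The handling of missing data could add to it. If non-attenders are more often lost to follow-up, (a) removes carried-forward baseline scores from the experimental arm while controls keep theirs. The SAP gives nothing from which to size this.

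What is at stake is how the results are read. Listed as checks on the ITT result, a similar or larger estimate from (a) or (b) would be taken as support, although selection alone could produce it. For (b) there is the further problem that two analysts following the SAP could build different data sets.

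**Working it through.** The SAP states no attendance rate, score gap, standard deviation, effect size or sample size, so there is no figure of its own to reproduce. The check has three parts.

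**1. Which participants each rule keeps**

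| Control condition | Set (a) | Set (b) |
|---|---|---|
| No sessions; test applied to everyone | attenders v. all controls | no controls, so no arm contrast |
| No sessions; controls pass because none were allocated | attenders v. all controls | completers v. all controls |
| Controls have their own sessions | attenders v. all controls | completers v. control completers |

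Column (a) assumes that controls are kept, as the name modified ITT implies. It is then one-sided in every row. Column (b) changes from row to row.

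**2. Size of the shift with no programme effect**

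Let *a* be the share of the experimental arm retained, and *g* the mean score of those retained minus that of those dropped, as it would be without any programme effect. The whole-arm mean is *a* × (retained mean) + (1 − *a*) × (dropped mean). With no effect, this equals the control mean in expectation. So

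bias = retained mean − whole-arm mean = (1 − *a*) × *g*.

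Both inputs are assumptions:

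| Share retained | g = 0.25 | g = 0.5 | g = 1.0 |
|---|---|---|---|
| 0.9 | 0.025 | 0.05 | 0.10 |
| 0.7 | 0.075 | **0.15** | 0.30 |
| 0.5 | 0.125 | 0.25 | 0.50 |

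Values are points on the 0–6 score. A negative gap gives the same sizes with the opposite sign, and *g* = 0 gives no bias. If (b) keeps all controls, the same formula applies with a share no larger than in (a). At 50% completing and a gap of 0.5, it gives (1 − 0.5) × 0.5 = 0.25.

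If both arms are filtered in (b), the bias is the experimental (1 − *a*) × *g* minus the control (1 − *a*) × *g*. It vanishes only if the two products are equal, which nothing in the SAP ensures.

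**3. A second model, as a check**

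Suppose attendance propensity is normal and correlates ρ with the outcome, and a share *p* attends. With no effect, the bias in SD units is ρ × φ(z)/p, where z = Φ⁻¹(1 − p). At p = 0.5, φ(0)/0.5 = 0.798, so ρ from 0.1 to 0.3 gives 0.08 to 0.24 SD. At p = 0.75 the range is 0.04 to 0.13 SD.

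With an assumed 100 randomised per arm and clustering ignored, the two-sided 5% false-positive rate becomes 7.5–28.2% at p = 0.5 and 5.9–13.2% at p = 0.75. With ρ = 0 it stays at 5%.

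**The case against.** A reader might infer that only the experimental arm can meet the attendance test, and that (b) therefore contains no controls. The SAP does not support this as a fact. It does not describe the control condition, which is properly left to the protocol. An empty control arm needs two things: that controls have no sessions, and that the reference to allocated sessions in (b) is read against its most workable sense, in which people allocated none are not tested. What stands is narrower: (b) has no stated control rule and supports at least three different data sets.

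The size is also open to challenge. Every input above is assumed, and even the sign of the gap is unknown. The composite gives the HIV-prevention point automatically to people with neither sexual nor injection risk, so low-risk non-attenders could score higher on that item. The planned drug-use-status covariate could absorb part of any gap. These points stand: the figures are illustrations, not estimates.

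Finally, ITT is primary, attender and completer analyses are common secondary looks, and the SAP says its list of sensitivity analyses is not exhaustive, so a better one could simply be added. The ITT result is indeed safe. But adding an analysis does not make (a) and (b) into robustness checks, and the SAP presents them under "We will carry out the following sensitivity analyses". Analysis (c) does not repair them either: it is a separate analysis, and alongside baseline measures it adjusts for post-randomisation variables such as GROV activities.

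**Conclusion.** The point holds in limited form. If controls are kept, (a) compares self-selected attenders with unselected controls on every reading. In (b), the control set is undefined. If controls are kept unselected, it has the same fault under a stricter filter. If both arms are filtered, it still conditions on a post-randomisation event.

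With no programme effect, the contrast in (a) is off by (1 − share retained) × the untreated gap, in either direction. The illustrative value is 0.15 points, and across the assumed ranges the size runs from 0.025 to 0.50 points. It is zero if attendance is unrelated to the score. Because the SAP fixes neither input, agreement between these sets and ITT is not evidence of robustness, and a larger estimate is not evidence of a stronger effect among attenders.

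The primary ITT estimate does not depend on any of this. The change is one the team should make, but the main conclusion does not rest on it.

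**What to change.** 1. State the control-arm rule for (a) and (b), including whether controls have sessions and what completing them means for a control.
2. Label both sets supplementary, not checks on the robustness of ITT.
3. Estimate the effect in attenders at the immediate follow-up with all baseline-completing participants kept, by one of two methods:
   - Weight controls on baseline predictors of attendance (principal-score weights). This assumes that those predictors account for the attendance-related gap.
   - Estimate a complier average causal effect with randomised arm as instrument and cohort clustering in the standard errors.
4. For the complier analysis, define receipt as at least one session or any GROV use. Leave out kit and naloxone requests: requesting naloxone is component (d) of the primary score, so counting it would define treatment partly by the outcome.
5. State the exclusion restriction: arm has no effect on people with neither a session nor GROV use. Kit availability is part of the package and could breach it, so this needs explicit comment. State also whether controls have GROV access.

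The cost is SAP wording and one further model. Session attendance and GROV use are already variables in the planned process analyses. The interval will be wider than in the naive attender comparison, and the result rests on the stated assumptions. If nearly everyone in the experimental arm uses some part of the programme and controls do not, the complier estimate will be close to ITT and say little about attendance itself.

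### Sensitivity analysis (c) assesses the robustness of a total effect by adjusting for uptake and delivery of the same package, so that part of it does not check the ITT result

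*SAP*

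**What the plan says.** The SAP's paragraph on the design states that the trial can assess the "total effect of the Zoom sessions, GROV app, and HIV/HCV testing and Narcan kit availability". It adds that "that test is possible only for the immediate follow-up and will be conducted in an initial outcome paper". The primary analysis compares experimental with control by ITT.

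Sensitivity analysis (c) starts with relevant baseline measures and then adds "GROV activities, intervention process evaluation, fidelity assessment, and HIV/HCV testing and Narcan kit shipment schedules as covariates to assess the robustness of the results". Robustness is the only purpose given. The SAP does not call this a mediation or direct-effect analysis, and it does not say what values control participants take on these covariates.

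Two other places bear on the point:

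- **Process analyses.** The SAP plans these separately, "examining the content of the sessions with ChatGPT 4.0 (or later versions) and testing if these variables"; the same sentence then continues "as well as the number of sessions attended and GROV use, correlate with the study outcomes in the intervention group". GROV use is therefore already analysed within the intervention group. Fidelity and process evaluation are not named there.
- **Shipment.** Component (d) of the primary composite is "requesting Naloxone before the assessment time point". As an example of a further sensitivity analysis, the SAP suggests "replacing the request data with the delivery/shipment data in the composite score".

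**The concern.** A total effect includes whatever the package achieves through being delivered and used. GROV activities, process evaluation and fidelity describe that delivery and use, and they come into being after allocation. Holding them fixed removes part of the effect being tested. It also brings in any common cause of uptake and outcome, such as motivation, against which randomisation gives no protection once uptake is conditioned on.

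At stake is how (c) will be read. A shift would be taken as evidence against the ITT result and agreement as support for it. Neither inference is warranted for these covariates, and which of the two appears can depend on a coding choice that the SAP leaves open.

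**Working it through.** The SAP gives no figure on this point, so there is none to reproduce. All numerical inputs below are assumptions chosen for illustration.

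**Step 1: sort the covariates in (c).**

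| Covariate | When it arises | Relation to the package |
|---|---|---|
| Baseline measures | before follow-up | none; valid check |
| GROV activities | after allocation | uptake of a named component |
| Process evaluation, fidelity | after allocation | delivery of the package |
| Kit shipment schedules | not clear | administrative timing, or individual uptake |

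**Step 2: the identity.** In OLS of the outcome on arm and uptake,

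adjusted arm coefficient = unadjusted difference - b × (mean uptake, experimental - mean uptake, control),

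where b is the pooled within-arm slope of outcome on uptake. The coefficient stays at the unadjusted difference only if b is 0 or mean uptake is equal in the two arms.

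**Step 3: controls at zero.** Assume a total effect of 0.50, outcome SD 1.3, 100 per arm, no clustering, and uptake with mean 1 and SD equal to CV (0.5 or 1.0) in the experimental arm and 0 in controls.

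- Unadjusted SE: 1.3 × sqrt(2/100) = 0.18.
- SE inflation: sqrt(1 + 1/(2 × CV²)) = sqrt(3) = 1.73 at CV 0.5 and sqrt(1.5) = 1.22 at CV 1.0. The adjusted SE is about 0.32 or 0.23.
- Half the effect mediated: b = 0.25, so 0.50 - 0.25 × 1 = 0.25.
- No mediation, but a common cause giving correlation r between uptake and outcome: b = r × 1.3/CV. At r = 0.2 this is 0.52 (CV 0.5) or 0.26 (CV 1.0).

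| Scenario (true total effect 0.50) | CV 0.5: formula / simulated | CV 1.0: formula / simulated |
|---|---|---|
| Half mediated | 0.25 / 0.247 | 0.25 / 0.247 |
| Common cause, r = +0.2 | -0.02 / -0.023 | 0.24 / 0.237 |
| Common cause, r = -0.2 | 1.02 / 1.017 | 0.76 / 0.757 |

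The simulated values come from 4000 OLS runs. With 10 cohorts of 10 per arm and ICC 0.05 (2500 GLS runs with the ICC taken as known) the coefficients are essentially the same. In the mediated case the SE rises from 0.22 to 0.34 (CV 0.5) or 0.26 (CV 1.0).

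**Step 4: dependence on control-arm uptake.** Take no mediation, r = +0.2 and an uptake SD of 0.5 in both arms, so b = 0.52.

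- Control uptake zero: 0.50 - 0.52 × 1 = -0.02.
- Control uptake half the experimental mean: 0.50 - 0.52 × 0.5 = 0.24.
- Equal uptake: 0.50 - 0.52 × 0 = 0.50.

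**Step 5: dependence on coding.** Centring uptake on the overall mean leaves the between-arm gap at 1, so the results of Step 3 are unchanged. Centring it within the experimental arm, with controls at 0, makes the gap 0, and the identity returns the unadjusted difference. In simulation the two differed by less than 1e-14 in OLS and in equal-cohort GLS. With a binary drug-use covariate and cohorts of 5 to 15, the median difference was below 0.002 and the largest 0.02 in 2500 runs.

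A delivery covariate with one value throughout the experimental arm and another throughout control is collinear with arm. The design matrix then has rank 2 for 3 columns, and the arm effect cannot be estimated.

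**Step 6: baseline covariates only.** A separate large simulation (n = 400,000, other assumed inputs, controls at zero) had a total effect of 1.0, half carried by uptake. It gave 1.00 unadjusted, 1.00 with a baseline covariate and 0.50 with uptake added. Under a true null with a positive common cause, the three values were 0.00, 0.00 and -0.50.

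**The case against.** The strongest replies are these.

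- **It is a sensitivity analysis, in a list the SAP calls non-exhaustive.** This stands, and it limits severity. A reader might infer that the ITT result is in doubt; nothing here supports that, because (c) does not alter the primary estimate.
- **Not all of (c) is at fault.** This stands. Baseline adjustment is sound, and because (c) speaks of analyses in the plural, separate models are possible. It would be too strong to reject (c) as a whole.
- **The figures rest on an inferred control arm.** This stands. That controls have no GROV use is plausible but not stated, and Step 4 shows the shift vanishing with equal uptake and no mediation. The figures show what can happen, not what is likely.
- **Agreement is exact only in a simple model.** This stands. The near-equality was checked for one uptake covariate with the ICC known, not for the SAP's selected random slopes or for several covariates jointly.
- **Agreement under (c) might be thought to hide a biased ITT estimate in a way the remedy would not.** That inference fails. A baseline-only model also misses an imbalance unrelated to its covariates. The narrower point is that centred uptake adds no check of its own.
- **Shipment.** A reader might infer that (c) adjusts for something close to an outcome component, since the SAP would accept shipment data in place of requests. But (c) refers to schedules, which may mean administrative timing. This calls for clarification and is not a demonstrated error.
- **Later visits.** The SAP confines the total-effect test to the immediate follow-up, so the conflict does not carry over unchanged to 3 and 6 months.

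None of these replies makes uptake or delivery of the package a test of whether its total effect is robust.

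**Conclusion.** The point holds for GROV activities, process evaluation and fidelity at the immediate follow-up, and it rests on the SAP's own statement of its target. Adjusting for them generally changes the quantity estimated, so neither a shift nor agreement in that coefficient bears on the robustness of the ITT result. On the assumed inputs with controls at zero, a true 0.50 ranged from -0.02 to 1.02; with within-arm centring it stayed at or very near the unadjusted value. Effect, SD, sample size, CV, correlation, ICC and control-arm uptake are all assumptions, so no size can be claimed for this trial. Severity is minor to moderate: the interpretation of one sensitivity analysis is affected and the primary analysis is not.

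**What to change.** - Limit the robustness check in (c) to baseline covariates that are named in advance.
- Move GROV activities, process evaluation and fidelity to the process analyses within the intervention group, adding the last two to the list there. Alternatively, keep the adjusted between-arm model as a separately labelled exploratory or mediation analysis, with its assumptions and control-arm coding stated, and do not present it as evidence of robustness.
- State what shipment schedules means. Keep it in the robustness check only if it is administrative timing independent of arm and of participants' requests. Do not adjust for individual shipment there, because the SAP offers shipment data as a substitute for the request component of the outcome.

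The cost is SAP wording and, if process evaluation and fidelity are moved, a few more exploratory analyses. No new data are needed. What is given up is reporting the uptake-adjusted between-arm estimate as a robustness check.

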Sum of Yes to (a) self-testing for HIV, (b) self-testing for HCV, (c) HIV prevention, (d) requesting Naloxone, (e) carrying Naloxone, and (f) making at least one social connection (new or reestablished).	HIV and HCV testing	Seeking substance use or mental health treatment or recovery services (i.e., attending a 12-step group or another abstinence-based program, attending a substance use treatment program that uses medications, and/or attending a faith-based substance use group and being referred to healthcare and mental health/substance use recovery)
	HIV prevention behaviors (i.e., PrEP use, use of condoms during sex, use of syringe service programs, and disinfecting injection equipment)	Interacting positively with people who use substances during and outside the sessions and drug stigma
	Requesting Naloxone (Narcan)	Substance use without a prescription or more than prescribed (with baseline level at 3 and 6 months)
	Carrying Naloxone (Narcan)	Injection substance use (with baseline level at 3 and 6 months)
	Making social connections (new or reestablished)	Seeking treatment for HIV and HCV if participant is seropositive

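### One tertiary outcome includes positive interactions during the sessions; if controls have no sessions, that part cannot be compared between arms and should move to the within-intervention process analyses

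*SAP*

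**What the plan says.** The opening paragraph of the SAP sets one comparison for all outcome tiers: "The statistical analyses will examine the intervention effect (i.e., experimental versus control) on the primary, secondary, and tertiary outcomes". In Table 1, the tertiary column contains the entry "Interacting positively with people who use substances during and outside the sessions and drug stigma". The SAP has no rule on how the in-session part, the outside-session part and stigma are scored, or whether they are combined. Nor does it exempt the in-session part from the arm comparison.

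Four places bear on who has sessions:

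- The paragraph on what the design can estimate describes the arm contrast at the immediate follow-up as an "assessment of the total effect of the Zoom sessions, GROV app, and HIV/HCV testing and Narcan kit availability".
- The modified ITT set is defined as "including only those experimental participants who attended at least one session".
- The process analyses look at session content and test whether these variables, "as well as the number of sessions attended and GROV use, correlate with the study outcomes in the intervention group".
- The later follow-ups are described as the period "when all participants have the option of receiving HIV/HCV testing and Narcan kits". Sessions are not part of that offer.

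The per-protocol set is worded differently, as "including only data from participants who completed all three Zoom sessions originally allocated", and names no arm.

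**The concern.** An outcome that is compared between randomised arms should be one that participants in either arm can have. Positive interaction during a session requires a session. If only the experimental arm has sessions, a difference on that part shows that sessions took place and were attended. It does not show that the programme changed how participants treat people who use substances. Randomisation does not help, because the difference would come from the definition of the outcome and not from imbalance between the arms.

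At stake is how one tertiary result is read. A difference that reflects exposure to sessions could be reported as a behavioural effect.

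**Working it through.** The SAP states no rate, sample size or power for this outcome, so there is no figure to reproduce. The check has two parts.

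**1. Do the sessions belong to one arm?**

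| Place in the SAP | What it implies |
|---|---|
| Total-effect paragraph | Sessions are one component of what the arm contrast measures. If controls had the same sessions, the contrast could not include their effect. |
| Modified ITT | The attendance condition applies to experimental participants only. |
| Process analyses | Session content and number of sessions attended are related to outcomes in the intervention group only. |
| 3- and 6-month paragraph | What becomes open to all participants is testing and Narcan kits; sessions are not listed. |
| Per-protocol set | No arm is named. Read literally, and with no sessions for controls, the set would contain no controls. |

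The first four point the same way and the fifth does not. The likely reading is that controls have no sessions, but this is an inference. What follows is conditional on it.

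**2. What does the in-session part do to the arm contrast?**

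*Scored alone.* The control rate is zero by design, or the item does not apply to controls. The contrast is then either a comparison with a fixed zero or has no control data. It is uninformative in both cases.

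*Combined with outside-session interaction.* Assume a yes/no outcome that is met in either setting. Let p be the outside-session rate, equal in both arms so that there is no true outside-session effect. Let q be the share of the remaining experimental participants who interact positively in a session. Then:

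- control rate = p
- experimental rate = p + (1 − p) × q
- difference with no outside-session effect = (1 − p) × q

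Both p and q are assumptions. Over a plausible grid the difference, in percentage points, is:

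| | q = 0.2 | q = 0.5 | q = 0.8 |
|---|---|---|---|
| p = 0.3 | 14 | 35 | 56 |
| p = 0.5 | 10 | 25 | 40 |
| p = 0.7 | 6 | 15 | 24 |

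For example, with p = 0.40 and q = 0.5 the experimental rate is 0.40 + 0.60 × 0.5 = 0.70, against 0.40 in controls. With q = 0.2 it is 0.40 + 0.60 × 0.2 = 0.52, against 0.40.

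*Scored as separate measures.* The outside-session contrast and the stigma contrast each carry an artefact of 0. Only the in-session contrast is affected, as in the first case.

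**The case against.** The strongest reply is that the SAP does not describe the control condition. A reader might infer that controls cannot score on the in-session part and that a difference is therefore certain. The text does not go that far. The per-protocol wording is not limited to one arm, and the protocol, which is not at hand, may give controls comparison sessions. In that case the point shrinks to unequal opportunity or disappears. This stands, and it is why the point is conditional. It does not remove the point, because the other four places favour sessions in the experimental arm only.

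A second reply concerns scoring. A reader might infer from the single table cell that behaviour and drug stigma are merged, so that a stigma effect could not be told apart from session exposure. The SAP does not support that. Table 1 groups several measures in other cells too, and where the SAP sums items, as in the primary outcome, it says so. Scoring detail is also commonly left to the protocol. This stands: stigma may well be scored separately, and it is then unaffected. It still leaves the in-session measure under the opening commitment to compare arms, where the comparison tells the reader nothing.

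Third, the percentages rest wholly on assumed rates and an assumed either-setting rule. That is correct. They show the mechanism and its possible range and do not estimate what this trial will find.

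Finally, the process analyses already give session content a place within the intervention group. That is true, but the SAP does not move this outcome there or withdraw it from the arm comparison.

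**Conclusion.** The point holds in conditional form. The SAP commits to an arm comparison of an outcome that includes behaviour during sessions, and its own text indicates that the sessions belong to the experimental programme. If controls have no sessions, the in-session part cannot support a between-arm conclusion. Alone it is uninformative; combined with outside-session interaction it adds (1 − p) × q. That is 6 to 56 points over the assumed grid, and 0 for outside-session interaction and stigma if these are scored separately.

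The conclusion rests on two things that the SAP leaves open: that controls have no sessions, and, for the numerical part, that the two settings are combined as yes/no for either. The outcome is tertiary and does not enter the primary composite, so the primary conclusion is unaffected. Priority is low.

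**What to change.** Change the tertiary column of Table 1 and add a sentence to the analysis text:

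- State that the between-arm comparison uses positive interaction outside the sessions only.
- List drug stigma as an outcome of its own.
- Analyse positive interaction during the sessions within the intervention group only, as part of the process analyses, where session content is already examined.

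This needs SAP wording only, provided that interactions in the two settings are recorded separately; that should be confirmed first. The price is that in-session interaction no longer contributes to a between-arm result. If the protocol shows that controls do have sessions, reporting the parts separately does no harm.
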